ACTH Treatment ACTH will be dosed by body surface area (BSA), with an initial dose of 80U per 1.73m². After 6 months of treatment, the initial dose will be reduced by 50% (1st reduction), to complete the second 6 months of ACTH therapy.

If patients develop significant side effects on the initial dose, they will have an early dose reduction by 50% at the discretion of each individual site PI (1st reduction). They will complete a total 6 months of treatment with the initial and reduced dose. After 6 months, ACTH will be reduced again by 50% (2nd reduction), to complete the second 6 months of ACTH therapy.

Patients who do not tolerate ACTH therapy despite an early dose reduction will exit the study with reporting of adverse events as appropriate.

Patients who relapse on a reduced dose of ACTH during the second 6 months of treatment will have their dose reverted to the previous dose and complete a total of 12 months of treatment with no further dose reductions.

Patients with two relapses on the highest tolerated ACTH dose will exit the study.

| BSA | Initial Dose | 1st Reduction (50%) | 2nd Reduction (25%) |
|------------|---------------------|----------------------------|----------------------------|
| 0.50-0.60 | 24U = 0.3mL | 12U = 0.15mL | 8U = 0.1mL |
| 0.61-0.75 | 32U = 0.4mL | 16U = 0.2mL | 8U = 0.1mL |
| 0.76-0.95 | 40U = 0.5mL | 20U = 0.25mL | 12U = 0.15mL |
| 0.96-1.09 | 48U = 0.6mL | 24U = 0.3mL | 12U = 0.15mL |
| 1.10-1.25 | 56U = 0.7mL | 28U = 0.35mL | 16U = 0.2mL |
| 1.26-1.45 | 64U = 0.8mL | 32U = 0.4mL | 16U = 0.2mL |
| 1.46-1.60 | 72U = 0.9mL | 36U = 0.45mL | 20U = 0.25mL |
| ≥ 1.61 | 80U = 1.0mL | 40U = 0.5mL | 20U = 0.25mL |

*Note: there is rounding of the doses to the closest administrable amount by subcutaneous injection.

Interval Visits

Telephone contact will occur weekly for the first 3 weeks after randomization. This will include screening for adverse events, reviewing medications and timing of medication changes, review of Albustix testing, and reviewing dosing of ACTH if applicable. Patients randomized to ACTH treatment will have two additional telephone contacts one month after ACTH dose reduction or discontinuation. This is to screen for symptoms of adrenal insufficiency.

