2. Cyclophosphamide or rituximab within the last 4 months.
3. Lactation, pregnancy, or refusal of birth control (abstinence qualifies) in females with child-bearing potential.
4. Planned treatment with live or live-attenuated vaccines once enrolled in the study.
5. Participation in another therapeutic trial concurrently or 30 days prior to randomization.
6. Active/serious infection (including, but not limited to Hepatitis B or C, HIV).
7. Malignancy concurrently or within the last 2 years.
8. Systolic or diastolic blood pressure >95% for age/height while receiving maximal doses of 3 or more medications.
9. Prior diagnosis of diabetes mellitus (Type I or II) or fasting glucose >200mg/dL
10. Organ transplantation
11. Contraindications to Acthar: scleroderma, osteoporosis, systemic fungal infections, ocular herpes simplex, recent surgery, history of or the presence of peptic ulcer, congestive heart failure, uncontrolled hypertension, primary adrenocortical insufficiency, or adrenal cortical hyperfunction
12. Secondary cause of nephrotic syndrome (e.g., SLE)
13. Biopsy demonstrating a diagnosis other than minimal change, FSGS or a variant (mesangial proliferation, IgM nephropathy)
14. Inability to consent/assent

Statistical Analysis

The primary end-point of the study and on which the statistical power is based is the proportion of patients who have a relapse in the 6 months following randomization to either ACTH or no ACTH.

We hypothesize that the 6 month relapse rate for patients receiving no treatment is 70%. In order to detect a 6 month relapse rate of 30% for patients receiving the ACTH gel, we will randomize 30 patients in each arm using a two sided z test with $\alpha=.05$. Our statistical power to detect such a difference is 91% which assumes two interim analyses at 50% and 100% of accumulated information. That is, once 30 patients have 6 month relapse data, we will conduct the first interim analysis. The last one will be completed once we have relapse data on all 60 patients. The table below gives the operating characteristics for such a design:

| Number of Patients with 6 Months Data | Boundary p-value |
|--|-------------------------|
| 30 | 0.006 |
| 60 | 0.045 |

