Treatment assignments will be stratified according to clinical center. The treatment assignments will be generated by the Data Coordinating Center (DCC) with the use of a pseudo-random-number generator with randomly permuted blocks that will be used to ensure balance between the number of subjects assigned to each treatment (ACTH or no ACTH). Before the study starts, the institutional research coordinator at each clinical center will be given a batch of

20 sealed, sequenced, opaque envelopes containing the treatment assignment and will have a unique ID consisting of the clinical center stratum.

Patients will be assigned to one of the two treatment arms in a ratio of 1:1.

Data Collection and Management

Data confidentiality

Information about study subjects will be kept confidential and managed under the applicable laws and regulations. Those regulations require a signed subject authorization informing the subject of the following:

- What protected health information (PHI) will be collected from subjects in this study
- Who will have access to that information and why
- Who will use or disclose that information
- The rights of a research subject to revoke their authorization for use of their PHI.

In the event that a subject revokes authorization, the Investigator, by regulation, retains the ability to use all information collected prior to the revocation of subject authorization. For subjects that have revoked authorization, attempts should be made to obtain permission to collect follow-up safety information (e.g. has the subject experienced any new or worsened AEs) at the end of their scheduled study period.

Data collection

Data collection and analysis will be facilitated by the Data Coordination Center (DCC), which will be led by [name]. They will interact with the PIs, local site investigators, and study coordinators to collect data, analyze the results, and provide reports to the DSMB in a timely manner.

REDCap will be used for data collection and management. The data collection system for this study uses built-in security features to encrypt all data for transmission in both directions, preventing unauthorized access to confidential participant information. Access to the system will be controlled by a sequence of individually assigned user identification codes and passwords, made available only to authorized personnel who have completed prerequisite training.

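### The 91% power and the final-analysis trigger both assume a 6-month outcome on all 60 children, but early exits can leave outcomes missing and the plan has no loss allowance or missing-outcome rule

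*Combined protocol and SAP*

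**What the plan says.** Participant Selection sets recruitment at sixty. Statistical Analysis assumes 6-month relapse rates of 70% without treatment and 30% on ACTH gel, and continues: "we will randomize 30 patients in each arm using a two sided z test". On power it says: "Our statistical power to detect such a difference is 91% which assumes two interim analyses at 50% and 100% of accumulated information". The boundary p-values are 0.006 at 30 patients and 0.045 at 60. On the final analysis it says: "The last one will be completed once we have relapse data on all 60 patients". The analysis is by assigned arm (intention to treat).

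Two rules elsewhere bear on whether 60 outcomes will exist:

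- ACTH Treatment: "Patients who do not tolerate ACTH therapy despite an early dose reduction will exit the study". Adverse events are then reported, but relapse follow-up is not mentioned. The early dose reduction is defined as one made before 6 months, so this exit can fall inside the primary window.
- Data confidentiality, on children whose authorisation is revoked: "attempts should be made to obtain permission to collect follow-up safety information". Relapse status is not part of that request, although information collected before revocation is kept.

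No section gives an expected exit rate, an allowance for loss, or a rule for a child without a 6-month outcome.

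**The concern.** Sixty are recruited, sixty carry the power, and sixty outcomes are required before the final test. The sample size therefore has no slack, while the protocol contains two routes by which a child can leave before the outcome is known. One of them exists only in the ACTH arm.

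Three things are at stake. The power used to justify the trial is a zero-loss figure that is not labelled as one. Read literally, the trigger fails after a single unobserved outcome. And intention to treat fixes the arm in which a child is counted, not the outcome assigned when none was seen. In an open-label trial with one-sided exits, the choice between dropping leavers and counting them as relapses should not be left until data are in view.

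**Working it through.** **1. Inputs (Statistical Analysis).** Rates 0.70 and 0.30; 30 per arm; looks at 15 and 30 per arm; two-sided boundary p-values 0.006 and 0.045, i.e. critical values c1 = 2.748 and c2 = 2.005.

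**2. Reproducing the 91% with no loss.**

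- Unpooled SE = √(0.7×0.3/30 + 0.3×0.7/30) = 0.1183
- Pooled SE = √(0.5×0.5×2/30) = 0.1291
- Drift θ = 0.40/0.1183 = 3.381
- Power = 1 − Φ₂(c1·r − θ√0.5, c2·r − θ; correlation √0.5), with r = 1 for the unpooled z and r = 0.1291/0.1183 = 1.091 for the pooled z

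| Method | Power |
|---|---|
| Normal approximation, unpooled | 91.7% |
| Normal approximation, pooled | 88.5% |
| Exact binomial enumeration, unpooled | 90.0% |
| Exact binomial enumeration, pooled | 89.7% |

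The stated 91% is reproduced within the choice of formula.

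**3. Which exits can lose the primary outcome.**

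| Exit | Outcome already known? |
|---|---|
| Two relapses on the highest tolerated ACTH dose | Yes; a relapse in the first 6 months is already the event |
| Control child choosing standard care | Yes; this follows a relapse |
| ACTH intolerance | Not if it precedes both a relapse and month 6 |
| Revoked authorisation | Not if it precedes both a relapse and month 6 |

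**4. What exits do to the rates.** Assumptions, none of them in the documents: a fraction d leave, evenly over 6 months; relapse times are exponential with the planned 6-month rates.

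*Counted as relapses.* The ACTH rate becomes 0.3 + 0.7d: 0.335, 0.370 and 0.405 at d = 5, 10 and 15%. With exits in both arms the control rate becomes 0.7 + 0.3d.

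*Dropped.* A child who relapses before leaving stays in; a relapse-free leaver goes out. An ACTH leaver has relapsed first with probability 1 − 0.3/0.3567 = 0.159, where 0.3567 = −ln 0.7. At d = 10% the analysed ACTH proportion is (0.9×0.3 + 0.1×0.159)/(1 − 0.1×0.841) = 0.286/0.916 = 0.312. At 15% it is 0.279/0.874 = 0.319. Dropping leavers therefore shrinks n and also raises the ACTH proportion slightly.

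**5. Power under assumed exits.** Simulation of the two-look design, pooled z, 200,000 trials per row:

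| Assumed exits | Leavers dropped | Leavers counted as relapses |
|---|---|---|
| None | 89.7% | 89.7% |
| 5% per arm | 87.4% | 86.3% |
| 10% per arm | 86.5% | 82.5% |
| 15% per arm | 85.1% | 78.0% |
| 5% ACTH only | 86.7% | 83.2% |
| 10% ACTH only | 84.7% | 75.1% |
| 15% ACTH only | 82.4% | 65.1% |

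With the unpooled z, dropping leavers gives about 90, 88 and 87% at 5, 10 and 15% per arm, and about 87 and 85% at 10 and 15% in the ACTH arm only. Counting leavers as relapses at 10 and 15% in the ACTH arm only gives 75.7 and 66.0%, so that fall does not come from the pooled formula.

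**The case against.** The other side has a good case on several points.

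- *The 91% is not an arithmetic error.* This stands. A reader might infer that the power was miscalculated; the documents do not support that. What is missing is a stated assumption.
- *No exit rate is given.* This stands. A reader might infer that the design delivers 82-87%, or as little as 65%. Those are results under assumed exits, and the lower range also needs an exits-as-relapse rule that the plan never states.
- *Part of the fall is formula.* Partly right. Shrinking n alone in the unpooled normal approximation, with 5-15% of ACTH children dropped, leaves 89-91%. That calculation omits the rise in the ACTH proportion from losing relapse-free leavers. With it included, the unpooled z still falls to about 85% at 15% ACTH-only exits.
- *Most exits do not matter.* Right for the two-relapse and standard-care exits. It would be wrong to say that the exit rules must prevent 60 outcomes; they can.
- *The trigger is ordinary wording for complete follow-up.* Fair as to intent: the Data and Safety Monitoring Plan also schedules one final analysis with a DMC meeting. A reader might infer that the trial could never be analysed, which overstates a wording fault. The sentence still does not say what happens when an outcome is missing.
- *Kaplan-Meier is not a free replacement for the primary test.* This stands. In simulation, the z test on Kaplan-Meier proportions with Greenwood variance had a type I error of about 6.1-6.3%, against 5.1-5.4% for the pooled z. With equal exits most of its apparent power gain is the variance formula. Leaving for intolerance is also unlikely to be non-informative.

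**Conclusion.** The point holds as a conditional one. The 91% and the final-analysis trigger both need a 6-month outcome on every randomised child. Intolerance exits and revoked authorisation can each leave that outcome unobserved, and the plan has neither a loss allowance nor a missing-outcome rule.

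If 5-15% leave evenly over 6 months, pooled z power is about 82-87% with relapse-free leavers dropped (about 85-90% unpooled) and about 65-86% with leavers counted as relapses. Dropping leavers keeps power above 80% throughout. The larger exposure is the unwritten rule: at 15% ACTH-only exits, the choice of rule moves power from 82% to 65%. The sizes rest on assumed exit rates, even exit timing and exponential relapse times. The direction does not depend on the exact rate.

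**What to change.** 1. **Statistical Analysis, power.** State it conditionally with the assumption shown, for example about 90% with complete data and about 85-87% if 10% leave before month 6 and are dropped.
2. **Statistical Analysis, trigger.** Run the final analysis when every randomised child has relapsed, reached 6 months or left the study.
3. **ACTH Treatment and Data confidentiality.** Reconcile the exit wording with the intention-to-treat analysis by collecting relapse status to month 6 after ACTH is stopped. Extend the permission request after revocation to relapse status. This concerns data collection only, not treatment.
4. **Primary analysis.** Keep the pooled z test, name it as pooled, and prespecify one rule for a missing 6-month outcome. Use Kaplan-Meier 6-month proportions and exits-as-relapse as sensitivity analyses only.

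The cost is a slightly less favourable stated power and a little more follow-up data. No patients are added.

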Using the method of Lan-DeMets, we list the boundary p-value for this sequential design. Thus, after our first interim look, we will reject the null hypothesis of equal 6 month relapse rates between ACTH gel and no treatment if our test statistic renders a p-value $< .006$. According to the intent to treat principle, patients will be analyzed according to the treatment they have been assigned to during the randomization procedure. The odds ratio of ACTH versus no ACTH, plus the Wald 95% confidence interval, will be also be calculated.

The primary end-point related to specific aim 2 is the proportion of relapse-free patients during the first 6 months and second 6 months of treatment with ACTH. This will include patients initially randomized to ACTH and patients who receive ACTH as rescue therapy following their initial relapse. We will estimate 6 month and 12 month relapse-free rate using the method of Kaplan-Meier and compare treatments using a log-rank test.

The primary end-point related to specific aim 3 is the proportion of patients who have relapses in the 6 months following completion of one year of ACTH. This will be compared to the proportion of patients with relapses during the initial 6 months in the patients randomized to no treatment using a z test statistic. Odds ratios of ACTH vs no ACTH will also be calculated.

We will also compare patients as randomized by secondary endpoints such as total prednisone exposure in 12 months, number of relapses, cholesterol and change in BMI with two sample t-tests. If normality assumptions do not hold, appropriate non-parametric methods will be used.

Growth data collected during the study will be summarized descriptively for each treatment group at each time point. Based on height data collected during the study and published reference height information, the height standard deviation score (SDS, also called z-score) will be computed for each patient at each time point as:

$$(\text{Height} - \text{mean height for that age category}) / \text{SD of height for that age category}.$$

Descriptive statistics of this endpoint will be presented by time point and the z-scores will allow identification of potential outliers.

Treatment Assignment and Randomization

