In addition to the completion of the appropriate forms, any serious adverse event or serious and unexpected suspected adverse reaction occurring during the study or in a post-study period of one month will be reported to the principal investigator, the Data Monitoring Committee (DMC), the local IRB, the sponsor, the study supporter, and participating sites within 2 business days. The IND sponsor will make an assessment of whether the event constitutes an unanticipated problem posing risks to subjects or others (UP). This assessment will be provided to the Emory University IRB, which, in turn will make a final determination. If the Emory IRB determines an event is a UP it will notify the appropriate regulatory agencies and institutional officials.

Adverse events that do not meet criteria for Serious Adverse Event will be reported using the Adverse Event Form during the follow up visit. Information regarding the diagnosis, date of occurrence, severity of the event, and therapy will be recorded. A determination of the relationship of the adverse event to the study participation will be made by the Participating Site investigator. Should a relationship be found, results will be reported to the sponsor, the study-supporter, and the DMC within 1 business week.

Data and Safety Monitoring Plan

An external Data Monitoring Committee (DMC) will be constituted prior to the randomization of the first patient. The DMC will consist of a minimum of three individuals outside the Division of Pediatric Nephrology. The individuals shall be practicing clinicians with experience in clinical research. At least one member will be a nephrologist, and two members will be pediatric subspecialists. Details on the membership, responsibilities and working procedures of the DMC will be described in the DMC Charter.

The DMC will perform the first safety review using a data cutoff 6 months after randomization of the first patient and every 6 months thereafter, unless otherwise requested by the Chairman of the DMC. The DMC will also receive reports on a regular basis on all SAEs reported for this trial. One interim analysis and one final analysis are planned. These analyses will coincide with the timing of the scheduled DMC meetings. Recruitment will not be interrupted unless otherwise requested by the Chairman of the DMC. Results of the DMC review will be shared with the PI and all participating sites within 1 business week.

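### The primary effect estimate takes no account of the look at 30 children: a result that crosses there must show a relapse odds ratio of roughly 7 to 11 or more (planned 5.4), reported with a fixed 95% interval

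*Combined protocol and SAP*

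**What the plan says.** All of this is in the combined protocol and SAP.

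- **Design values (Statistical Analysis).** "We hypothesize that the 6 month relapse rate for patients receiving no treatment is 70"%. The ACTH rate to be detected is 30%, and "we will randomize 30 patients in each arm using a two sided z test". "Our statistical power to detect such a difference is 91"%.
- **Looks (Statistical Analysis).** "once 30 patients have 6 month relapse data, we will conduct the first interim analysis", with boundary p-value 0.006; the final analysis at 60 has boundary 0.045. The boundaries are attributed to Lan-DeMets.
- **Estimate for the primary comparison (Statistical Analysis).** "The odds ratio of ACTH versus no ACTH, plus the Wald 95% confidence interval, will be also be calculated". No bias-adjusted estimate, no interval tied to the boundaries and no interval for the difference in proportions is described. Aims 2 and 3 have their own estimates (Kaplan-Meier rates and odds ratios).
- **Stopping (Data and Safety Monitoring Plan).** Stopping is a judgement of the DMC and the PI, in which the interim analysis may count. "Recruitment will not be interrupted unless otherwise requested by the Chairman of the DMC".

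**The concern.** With about 15 children per arm and a threshold of p < .006, only very large observed differences can cross. Results reported after an early stop are therefore selected for being large. An ordinary odds ratio from those children overstates the effect on average unless the true effect is itself very large, and a fixed 95% interval uses a looser level than the 99.4% at which the decision was taken.

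The protocol's abstract notes that nothing has been published on this gel in children with nephrotic syndrome. An early-stop estimate from this trial could therefore become the reference figure for its size of benefit, with nothing in the report to show the selection.

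**Working it through.** **Inputs.** From Statistical Analysis: relapse 70% and 30%, 30 per arm, two-sided z test, boundaries 0.006 (|z| > 2.748) and 0.045 (|z| > 2.005). Two things are not stated and are treated as assumptions: whether the z test uses a pooled or unpooled variance (both shown), and the split at the look (15:15 here; 14:16 and 13:17 also checked, since Treatment Assignment and Randomization gives 1:1 blocks within centre, which does not guarantee 15:15). Odds ratios are written as no ACTH versus ACTH, so values above 1 favour ACTH.

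**Step 1, the plan's own power.** Unpooled drift = 0.40 / √[(0.70×0.30 + 0.30×0.70)/30] = 3.38. The two-look normal calculation with the printed boundaries gives 91.7%. A simulated two-look design with pooled z gives 89.7%. The stated 91% is reproduced within 2 points and does not settle which variance was meant.

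**Step 2, planned odds ratio.** (0.70×0.70)/(0.30×0.30) = 5.44.

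**Step 3, smallest result that crosses at 30.** All 16 × 16 tables at 15:15 were listed and those with z > 2.748 kept.
- Pooled: 11/15 versus 3/15 (or 12/15 versus 4/15), p = 0.0034, odds ratio (11×12)/(4×3) = 11.0. The smallest crossing difference in any table is 7/15 = 47 points.
- Unpooled: 11/15 versus 4/15, p = 0.0039, odds ratio (11×11)/(4×4) = 7.6. The smallest crossing difference is 40 points.
- Across all the splits checked, the minimum runs from 7.3 to 11.0. Every variant exceeds 5.44.

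**Step 4, what is reported given crossing.** Each table is weighted by its exact binomial probability. The Wald interval is exp(ln OR ± 1.96 × SE), with SE = √(1/a + 1/b + 1/c + 1/d).

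| True rates | Variance | Crosses | Mean difference | Median OR | 95% OR interval covers |
|---|---|---|---|---|---|
| 70% v 30% (40 points, OR 5.44) | pooled | 28.7% | 60 points | 16 | 97% |
| | unpooled | 43.4% | 55 points | 11 | 98% |
| 70% v 40% (30 points, OR 3.5) | pooled | 12.9% | 58 points | 16 | 83% |
| | unpooled | 22.7% | 53 points | 11 | 91% |
| 70% v 50% (20 points, OR 2.33) | pooled | 4.7% | 55 points | 16 | 69% |
| | unpooled | 9.6% | 51 points | 11 | 85% |

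Leaving out tables with an empty cell, or adding 0.5 to those tables only, moves coverage by less than one point. Adding 0.5 to every table raises the pooled 83% to 94% and leaves the 69% unchanged, so the middle scenario depends on that convention.

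**Step 5, over all trials.** With pooled z at the planned effect, the mean difference is 43 points against 40. Coverage is about 95% or higher in all three scenarios.

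**Step 6, one marginal result.** For 11/15 versus 3/15, ln OR = 2.398 and SE = √(1/11 + 1/4 + 1/3 + 1/12) = 0.870. At 95%: exp(2.398 ± 1.96×0.870) = 2.0 to 61. At the boundary's level: exp(2.398 ± 2.748×0.870) = 1.0 to 120.

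**Step 7, candidate remedies.** Coverage given crossing, pooled z, truth 70% versus 30 / 40 / 50%:
- odds ratio at 99.4%: 100 / 99.9 / 99.7%
- Wald risk difference at 99.4%: 96 / 90 / 72%
- Newcombe risk difference at 99.4%: 97 to 99.9% over the three

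If N children have been randomised when the trial stops, and those beyond the 30 carry the true 40 points, the pooled-z mean difference becomes (0.597×30 + 0.40×(N−30))/N: 0.531 at N = 45 and 0.498 at N = 60. Accrual is not stated, so 45 and 60 are assumptions.

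**The case against.** The strongest reply is that little goes wrong under the design as planned. At 70% versus 30% the 95% interval covers in about 97-98% of crossings, and the average over all trials is off by about 3 points. The low coverage arises at smaller true effects, which cross less often. This stands, and it limits the interval problem to effects smaller than planned. It does not remove the 15 to 20 point excess in the point estimate at the planned effect.

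Second, crossing is a rejection rule and not an automatic stop, recruitment continues by default, and analysis is by intention to treat. A reader might infer that an early report would rest on the first 30 children alone. The documents do not say so; they are silent on which children would count. That silence is what needs filling.

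Third, a reader might infer that the odds ratio is the wrong measure because it looks much larger than the risk ratio (0.70/0.30 = 2.3) for so common an outcome. That is a property of the measure and largely a reporting choice. The end-point is the proportion relapsing in each arm, so the difference can be read off directly; only its interval is missing. Step 7 also shows that moving to a Wald risk difference would lose much of the coverage that a wider odds-ratio interval restores.

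**Conclusion.** The point holds for results reported after a stop at 30, and only for those. The plan provides an early efficacy look but no estimate or interval that allows for it. At the planned effect, 29% to 43% of trials would cross, with an average overstatement of 20 points (pooled) or 15 points (unpooled).

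A reader might infer a firm 11-fold minimum. That needs a pooled variance and a 15:15 split, neither of which the documents state; roughly 7- to 11-fold is what they support. A reader might also infer that the trial's inference is unsound. It is not: on the normal approximation, boundaries 0.006 and 0.045 together spend 0.0475 two-sided, so type I error is controlled. What suffers is the reported size of the effect, and the interval's coverage if the true effect is smaller than planned. That no adjustment is intended is read from the plan's silence.

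**What to change.** Three changes to the Statistical Analysis text:

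1. If the trial stops after the look at 30, compute the reported primary effect from all children randomised by then, each followed to month 6, and show the 30-child result as the interim finding. Under the assumptions in the working, this brings the mean difference from 60 down to about 53 or 50 points.
2. Replace the fixed 95% with the level of the boundary used: 99.4% at the look, 95.5% at the end. If a risk difference is added, give it a score-based (Newcombe) interval at the same level, not a Wald one.
3. State whether the z test is pooled or unpooled and how empty cells are handled, since both change the figures.

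Cost: wording only, with no added patients and no change to the boundaries. After an early stop the interval is 2.748/1.96 = 1.40 times as wide on the log-odds scale; at the final analysis the factor is 2.005/1.96 = 1.02. The final report of an early stop would wait for follow-up to finish.

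Two limits should be stated. The wider interval restores coverage but does not correct the point estimate; only the first change reduces that bias, and only as far as accrual allows. And with an unpooled test, a marginal crossing can give an interval that includes 1: for 11/15 versus 4/15, SE = √(1/11 + 1/4 + 1/4 + 1/11) = 0.826, so exp(2.023 ± 2.748×0.826) runs from 0.78 to 73. The plan should say in advance that the z test decides.
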